Appendix B

Constant Work Rate Exercise Test

Two operators will be present during the test. If the patient has cardiac issues or other clinical conditions which may be of concern then a doctor will be present. Before booking the appointment, ensure supervising doctor is available if appropriate.

Equipment Setup

Before patient testing, prepare the following;

- Mouthpiece for spirometry
- Serial sheet for spirometry
- CPET data sheet (located in the top drawer under the fridge)
- Mask (prepare a range of sizes)
- Flow head (located in plastic box on shelf on right of door)
- White ring adapter (located as above)
- ECG box (located as above)
- ECG electrodes (located in cupboard above the left of the sink)
- Skin prep pads (located as above)
- Ensure there is paper in the printer and the flap below is pulled out to catch it
- Ensure fan in room

- Print the patient referral (go to workbench on Trak, highlight patient + select print at the top of the page)
- Check if the patient has been before – if they have the patient should be tested at the same wattage

To Start System

Open gas cylinder and ensure adequate gas and pressure

Turn on system by pressing button on bottom right of the right hand monitor

Double click on “Breeze” icon on left hand screen to open program

Enter Login Name and Password and press “OK”

Ensure vacuum pump is on. If not, press “Vac” at the top of the screen (if the timer is stuck at 30:00, the vacuum pump is probably off)

Turn on the bike using the switch at the back below the seat

Calibration

Press “Calibrate” at the top of the screen

Take the 3L syringe from below the left hand side of the desk and attach the flow head to the blue rubber end with the side containing the holes facing into the syringe

Connect the umbilicus to the top of the flow head

Press “zero flow”

Press “start”

Withdraw and inject as directed until “calibration successful” is displayed

Replace the umbilicus to the port with the patterned side up

Remove the flow head and replace the syringe

Press the “O2 and CO2 analysers” tab

Click “calibrate” and wait until “calibration successful” is displayed

Click “OK” at the bottom left of the screen

Patient Details

For Existing Patients-

Click on yellow folder (Open Patient) to search for the patient.

Select Find.

Click on the drop down menu for search options, i.e. Name, ID etc.

Enter the search option selected to search for the patient.

If the patient is found it is highlighted.

Select Open and then add visit

Enter patient demographics and history as necessary.

Ensure that “GX Predicted Set Selection” has the option “Glaser” selected

For New Patients-

Search first as above, if not found, close that window.

Click on White folder (new Patient)

Enter all patient details.

Then select Add Visit.

Enter more details as necessary (Height, Weight, Requesting Physician/Unit, Site and Physiologist are Mandatory)

Ensure that “GX Predicted Set Selection” has the option “Glaser” selected

The Patient History tab should be used to enter more details, e.g. medication and clinical details, smoking history etc.

To close any patient demographic window, click on the yellow open folder to close.

Preparing the Patient

Check patient details and measure height and weight (NB Maximum weight for bike is 160kg).

Check with patient for any contraindications to testing.

Contraindications for Testing

- Recent/Acute M.I
- Unstable Angina
- Chest Pain
- ST depression > 2mm on resting ECG in most leads
- Uncontrolled hypertension at rest (>180/100 mmHg)
- Uncontrolled arrhythmias
- Severe Aortic Stenosis
- SpO₂ < 80% at rest

Perform SVC and FVC manoeuvres as per SOP in section 3 folder. A white ring adapter is required to connect the flow head to the mouthpiece. If the spirometry was performed on box, predicted values must be refreshed – Click edit, then “rerun predicted values”.

Fill in the CPET data sheet, including the predicted HRmax (220-age) and predicted Vemax (40 x FEV1).

Explain the test to the patient, e.g. “You are going to be doing a bicycle exercise test but we are going to monitor several things whilst you exercise. You will have electrodes on your chest to monitor your heart, a blood pressure cuff on your arm for your blood pressure, a small clip on your ear lobe to monitor your oxygen saturation and a face mask which will measure your breathing pattern and oxygen consumption. We will get you on the bicycle first, just breathing for 1 minute before we start you exercising and then there will be a warm up period of 3 minutes easy pedalling. **Then we remain a constant workload at 75% of the maximal work load obtained from the maximal CPET (CPET) conducted before. We want you to really push yourself and do as much as possible.**”

Prepare earlobe with a vasodilator cream for pulse oximeter probe.

Stickers (called electrodes) and a band will be put onto the chest of the patients by themselves to monitor their heart rate and rhythm, therefore, their privacy will be ensured. Some men may need to have a small area of their chest shaved in order for the electrodes to stick to the skin. Seat patient on bike.

Check height of bike and adjust as necessary using the up and down arrows on the bike unit until the patient’s extended leg has a slight bend at the knee. The handlebars can also be adjusted by loosening the black handles on handlebar unit. (If the screen displays a menu, select PC Mode)

Attach ear probe for oximetry and run the cable over the hook on the back wall to ensure it stays out the way.

Fit the blood pressure cuff by feeling for the brachial pulse and fitting the orange tab over it, 2-3cm above the cubital fossa. Secure the cable through the Velcro on the handlebars.

Fit mask over the patient’s face. To ensure no leaks, instruct the patient to breathe in maximally then cover the hole in the mask with the palm of your hand as they exhale. Repeat with patient inhaling against the palm of your hand.

Establish appropriate workload for patient (at 75% of the maximal work load obtained from the maximal CPET conducted before).

Patient Testing

Click the “GX” tab at the bottom of the screen

Under “Script Name”, select “JAI”

Select the desired work rate increment by choosing the appropriate ramp under “default protocol”

Ensure that “Borg Scale” is selected to “6-20”

Click on “summary” to gain a value for VO₂ Max and write this on the CPET data sheet

Select the “test” tab at the bottom of the screen

Turn on SpO₂ monitor

Ensure the umbilical is connected to the black port located below the screen to the left and click “Gas AutoCal”.

Then plug the umbilical into the flow head and strap it over the patients head onto the headpiece

Click on the ECG icon on the right hand computer screen

Turn on the ECG box by pressing the button on the front of box

Observe the ECG

Press **Start**

Keep patient still on the bike

Take a resting BP measurement by pressing the red droplet with a circle inside

Record resting BP along with SpO₂ and HR on the CPET data sheet

Click on ECG event icon

Change Mason-Likar to “interpret all”

Monitor resting ECG for any abnormalities

Press **Exercise**

Instruct the patient to begin pedalling at 70 rpm

Take a baseline BP measurement by pressing the red droplet with a circle inside

Record baseline BP along with SpO₂ and HR on the CPET data sheet

After three minutes, tell the patient that the workload will remain constant at 75% of the maximal work load obtained from the maximal CPET conducted before.

The system will automatically take BP measurements approximately every 3 minutes – these must be recorded along with SpO₂ and HR on the CPET data sheet

Encourage the patient throughout to perform maximally

Observe all parameters throughout, especially the ECG for ST depression or arrhythmias, but also to pick up any erroneous measurements arising from technical factors e.g. low VO₂ from a leak etc.

Terminate the test if the patient fulfils any of the termination criteria;

Termination Criteria

- Maximal test – patient could not do any more
- Progressive Chest Pain
- Oxygen desaturation to below 80%
- Hypotension, drop in systolic blood pressure or failure of BP to rise through exercise.
- Severe Hypertension (>250/120 mmHg)
- More than 2mm ST segment depression (horizontal or negative sloping)
- 3mm ST depression (positive sloping)
- Progressive ST segment elevation
- AV Block
- Frequent Ventricular Ectopic or Ventricular Arrhythmias
- Rapid Supra-ventricular Arrhythmias

Press Recovery

Click recovery as soon the patient stops

Take a BP at beginning of recovery, and every three minutes until baseline HR and SpO2 values are reached again

Press Stop

Ask the patient what made them stop the test and record on the CPET data sheet

Give the patient a Borg Score scale for perceived exertion and record on CPET data sheet

Click on ECG icon to stop ECG

Turn off ECG by pressing the button on the box

Printing Results

ECG

Click “page review”

Deselect ectopic etc. unless you want to print an example of something specific

Press the running man icon at the top of the right hand screen

Press “preview”

At the top left of the left hand screen, deselect all tick boxes except “exam summary”, “rate/BP/workload trends” + “peak averages”

Click “refresh” at the bottom left of the screen

Click the “X” at the top right of the screen

Click “save” and then “exit”

Click the save icon on the right hand screen

AT

Click the AT tab at the bottom right of the screen

Move the AT line to the correct position

To view other graphs press F12

Click “save”

Print

Select Quick Print from menu bar at top of screen

Select “JAI Report”

Cleaning

Place ECG electrodes in the domestic waste bin

Wipe down;

- Bike
- BP cuff
- SpO2 sensor
- ECG box

Clean in the basin located under the sink with hot, soapy water;

- Mask
- Flow head
- Headgear

Hang the headgear from the hooks on the back wall

Prepare descogen by filling the appropriate lidded container with water and adding one scoop of descogen and place the mask and flow head in. Leave for 20 minutes then rinse and place on the side to dry

Closing down the System

Close the patient

Exit the program

Shut down the computer

Close the gas cylinders

Turn off the bike using the switch at the back

Reviewing Results

Open patient file to be reviewed.

Highlight date of tests to be reviewed and select Open visit.

Click on tab to review particular test results.

To see graphical display for test results, highlight the test time

Reviewing Reports

Open patient file to be reviewed.

Highlight date of tests to be reviewed and select Open visit.

Select Quick print from top menu bar.

Select Report switchboard.

Select appropriate report, e.g. JAI report

Select Preview to display the report

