3 OUTCOME MEASURES

3.1 PRIMARY OUTCOME

The primary outcome will be Exercise Capacity, which will be assessed as endurance time (Tlim) during a constant work rate cycle test at 75% of the maximal workload (obtained beforehand from a maximal CPET).

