4.9 BLINDING

In this open label study patients will not be blinded with respect to the modality of oxygen delivery but will not know the dose of oxygen they will be receiving or their SpO2 during the pulmonary rehabilitation program and the tests.

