4.12 DATA COLLECTION

The UK General Data Protection Regulation (GDPR) requires appropriate technical and organisational measures to be in place to implement the data protection principles effectively and safeguard individual rights. This is ‘data protection by design and by default’.

In essence, this means we will integrate or ‘bake in’ data protection into our processing activities and business practices, from the design stage right through the lifecycle.

4.12.1 Data to be collected:

- Weight
- Height
- Blood Test (blood biomarkers associated with the progression of the fibrosis)
- Blood Pressure
- QMVCT (Strength of the Quadriceps muscle measured in Newtons)
- mMRC (score of dyspnoea from 1 to 5)
- CPET (Maximum workload measured in watts)
- CWRCT (time or exercise tolerance measured in minutes)
- Physical activity levels in daily life (measured in steps)
- SGRQ (Score of this questionnaire that measures the QoL)
- HADS (Score of this questionnaire that measures anxiety and depression levels)

4.12.2 Time points for collection: these data will be collected during the baseline and post intervention appointment by the CI ([name]) and the PI ([name]) in Edinburgh and by [name] (Physiotherapist) in Newcastle.

4.12.3 Details of standardised tools to be used:

- Modified version of the Medical Research Council scale (mMRC): see appendix D.
- Saint George Respiratory Questionnaire (SGRQ): see appendix E.
- Hospital Anxiety Depression Scale (HADS): see appendix F.

4.12.4 Methods to maximise completeness of data: PI will call participants who have not returned questionnaires.

4.12.5 How will data be recorded Data will be recorded using both eCRF and pCRF.

4.12.6 Source Data Documentation: Source data is defined as all information in original records and certified copies of original records or clinical findings, observations, or other activities in a clinical study necessary for the reconstruction and evaluation of the study. Source data are contained in source documents.

Source documents are original documents, data and records where source data are recorded for the first time.

We will use the medical records from Trak to obtain information of the high resolution computed tomography (HRCT) of the thorax, echocardiograms, breathing tests including Spirometry, Lung volumes and DLCO.

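### The effort-limited primary endpoint is measured under unscripted encouragement, and nothing keeps the person giving it unaware of the arm

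*Protocol*

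**What the plan says.** Section 3.1 of the protocol defines exercise capacity, the primary outcome, as "assessed as endurance time (Tlim) during a constant work rate cycle test". Appendix B heads its termination criteria for that test with "Maximal test – patient could not do any more"; the other criteria are safety limits.

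On conduct of the test, Appendix B states "Two operators will be present during the test" without naming their roles, and instructs them: "Encourage the patient throughout to perform maximally". The only wording it supplies is an example explanation read before the test, which ends "We want you to really push yourself and do as much as possible". Nothing is supplied for use during the test.

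Section 4.12.1 lists the constant work rate test time among the data to be collected. Section 4.12.2 says "these data will be collected during the baseline and post intervention appointment by the CI" and the principal investigator in Edinburgh, and by a physiotherapist in Newcastle.

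Section 4.9 says "In this open label study patients will not be blinded with respect to the modality of oxygen delivery". The only masking it adds is that patients are not told their oxygen dose or saturation. It does not mention assessors. Section 4.8 places randomisation before any baseline procedure.

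**The concern.** Tlim depends on how hard the patient is willing to push, and verbal prompting acts directly on that. Appendix B goes into detail down to individual button presses, yet leaves the prompting to the operator. If the operator knows the arm and hopes that HFNO works, patients in that arm may be urged on more strongly or more often. The extra time would then be read as a treatment effect on the primary endpoint. Section 6 plans a t-test at the 0.05 level in about 30 patients, and such a test cannot tell a shift due to encouragement from a shift due to treatment. How the test is conducted is settled in the protocol and its appendix, and a later analysis plan cannot supply it.

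**Working it through.** The protocol gives no sample size calculation, target effect or SD for Tlim (section 6), so there is no figure to reproduce. The check has two parts.

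**1. Is there a route for bias?**

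| Question | Where | Answer |
|---|---|---|
| Does effort decide the endpoint? | 3.1; Appendix B | Yes. Unless a safety limit is met, the patient's own exhaustion ends the test. |
| Is encouragement required? | Appendix B | Yes, throughout the test. |
| Is it standardised? | Appendix B | No. There is only an example pre-test explanation. |
| Who collects the time? | 4.12.1, 4.12.2 | Chief and principal investigators; physiotherapist at the second site. |
| Does an allocation exist when the test is run? | 4.8; schedule in 4.11 | Yes, at both visits. |
| Is the prompting operator kept unaware of it? | 4.9, 4.12.2, Appendix B | No provision. |
| Would the test set-up reveal the arm? | 4.7 | Not necessarily. Oxygen at the assessment visits is by nasal cannula when needed, with no difference by arm stated. |

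The route is therefore open. The last row shows that it could be narrowed.

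**2. What would a given shift do? (illustration)**

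Inputs from section 6: about 30 patients, Student's t-test, significance level 0.05. Assumptions: 15 per arm (the 15 in section 4.2 is per site), a two-sided test, no true treatment effect, and a pure encouragement shift of b SD towards HFNO.

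Degrees of freedom: 15 + 15 − 2 = 28. Critical value: t(0.975; 28) = 2.048. Smallest significant difference: 2.048 × √(2/15) = 0.75 SD.

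Chance of a significant result favouring HFNO = 1 − F(2.048; 28, λ), where F is the noncentral t distribution function and λ = b × √(15/2) = 2.739 b.

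| Assumed shift b (SD) | λ | Chance of false significance favouring HFNO |
|---|---|---|
| 0 | 0 | 2.5% |
| 0.1 | 0.27 | 4.5% |
| 0.2 | 0.55 | 7.6% |
| 0.3 | 0.82 | 12.2% |
| 0.5 | 1.37 | 26.2% |

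Nothing in the protocol says which row applies. Expressing b in seconds would need a typical test length and an SD, and the protocol gives neither.

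**The case against.** The strongest reply is that this is a declared open-label proof-of-concept study, that the encouragement instruction is the same for both arms, and that the protocol nowhere says a partial person runs the test. Part of this stands, and it limits the point in four ways.

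- **Who runs the test and what they know.** A reader might infer that the investigators and the physiotherapist themselves ride the patient through the test knowing the arm. The protocol does not say so. Section 4.12.2 makes them collectors of a list that also covers weight, blood tests and questionnaires. Appendix B names only two operators and makes a physiologist a mandatory entry, so laboratory staff may run the bike. Confirming eligibility before randomisation (section 4.8) shows nothing about knowing the arm afterwards. What can be said is that nothing prevents it.
- **Stopping the clock late.** A reader might also suspect a later stop in the HFNO arm. Appendix B has recovery triggered the moment the patient stops, and many of its safety limits are numerical. The plausible route is encouragement.
- **Whether the data could show it.** It would be too absolute to say that nothing could be examined afterwards. Appendix B records heart rate, saturation, a Borg score and the reason for stopping. These permit a comparison of effort between arms, though not a correction of the bias.
- **Direction.** Section 1.2 expects HIIT with HFNO to help. That is an ordinary hypothesis, and both arms receive HIIT (sections 4.1 and 4.10). It makes a bias towards HFNO likelier than the reverse but does not demonstrate partiality.

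The open-label label itself is not an answer. It is unavoidable for patients and for whoever trains them, but not for the person who prompts during a test done on the same type of cannula in both arms. An instruction that is common to both arms but has no content does not ensure equal encouragement.

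**Conclusion.** The concern holds as a risk of bias that the protocol leaves open and could cheaply reduce; it is not a demonstrated bias. It rests on three facts in the text: an effort-limited primary endpoint, required encouragement without fixed wording or timing, and no provision for masking the person who gives it. That this person will know the arm is an inference from the open-label design and from randomisation before baseline.

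The likely direction favours HFNO, but the size is unknown. The probabilities above show only what an assumed shift would do with 15 per arm and are not an estimate for this trial. The change should be made, but it does not block the study. Patients' own knowledge of their arm is a separate source of bias, which remains whatever is done about the operator.

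**What to change.** - **Appendix B.** Replace the open encouragement line with one fixed phrase spoken at fixed intervals, identical in both arms and at both visits. Leave the safety termination criteria unchanged.
- **Sections 4.9 and 4.12.2.** State that, where existing staffing allows, the one of the two required operators who speaks the phrase and records the time at the post-intervention test did not train that patient and has not been told the arm. Ask patients not to reveal it. Record for each test whether that operator was masked.
- **Limitation.** Acknowledge that patient expectation in an open-label trial is not removed by these steps.

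The script costs almost nothing. Masking needs some rostering effort, and the protocol does not describe staffing at either site, so it may not always be possible without extra staff. Where it is not, the script alone applies.

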Appendix C

Administration of Oxygen through HFNO and Nasal Cannula.

High Flow Nasal Oxygen is a System which delivers heated, humidified high flow oxygen therapy via nasal cannula or tracheostomy attachment. HFNO has become increasingly used for management of patients with type 1 respiratory failure. It delivers high inspiratory gas flow (up to 60 litres per minute), which is warmed and humidified. Oxygen can be titrated from 21-95%. If oxygen exceeds 95%, the oxygen reading will pulse red and the device will alarm.

Benefits include:

- Reversal of hypoxaemia
- Reduced work of breathing
- Improved secretion clearance
- Improved patient tolerance/ comfort

Absolute Contra-indications

- Patients with type 2 respiratory failure requiring Non-invasive ventilation (NIV)
- COVID or suspected COVID infections
- Nasal passage abnormalities or recent nasal surgery
- Cerebro-spinal fluid leaks
- Basal skull fractures
- Severe epistaxis

Equipment

- Fisher & Paykel AIRVO2 TM humidifier

- Opti-flow nasal cannula (small, medium or large) or Tracheostomy Direct Connection. A mask could be used if other options are not appropriate

- Heated breathing circuit and water chamber
- 1l bag of sterile water
- Bubble oxygen tubing

Setting patient up on the HFNO

- Explain procedure to patient/ carer and gain consent.
- Wash hands and wear appropriate Personal Protection Equipment (PPE) in line with infection control policy.
- Assemble equipment as per manufacturer's instructions. Label equipment with date for tubing change (according to manufacturer's instructions). All disposable components are single patient use. Select appropriate patient inter-face. Switch equipment on, connect oxygen supply if required and check it is ready for use (check disinfection status).
- Perform sounding alarm test by disconnecting tube from top of machine to check that alarm sounds.

Adjusting settings

- Press any button to enter the summary screen. Select temperature using the arrow right button. Press and hold down both the up and down arrows at the same time to unlock the screen. Use up and down arrows to select desired temperature. Ideally should be set at 37°C as this will provide optimum humidification but this may not be comfortable so either 34 or 31°C may be selected, if a mask is used then temperature should be set at 31°C.
- Press the arrow right button to select flow rate screen. Unlock screen as above. Use up and down buttons to select required flow rate. All patients will receive 50 lpm flow to maintain a saturation of oxygen $\geq 88\%$.
- Press the arrow right screen to access oxygen percentage and use the attached flow meter to adjust the percentage of oxygen until required patient saturations are reached. The screen does not require unlocking to adjust the oxygen percentage.

Cleaning of equipment

- Once therapy has been discontinued discard all disposables in appropriate waste.
- Clean as per manufacturer's instructions including a disinfectant cycle.

Nasal Cannula

Oxygen through nasal cannula will be delivered to maintain an oxygen saturation $\geq 88\%$.

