4.4 EXCLUSION CRITERIA

1. - Emphysema greater than extent of fibrosis on high resolution computed tomography (HRCT) of the thorax.
2. - FEV1/FVC ratio < 70%.
3. - Participants should not be taking part in other interventional studies currently. Our research is not a CTIMPs and co-enrolment will not be allowed under any circumstances.
4. - Absolute contraindications for cardiopulmonary exercise testing, which are:
 - a. - Unstable angina
 - b. - Uncontrolled arrhythmias causing symptoms or hemodynamic compromise.
 - c. - Syncope.
 - d. - Active endocarditis.
 - e. - Acute myocarditis or pericarditis.
 - f. - Symptomatic severe aortic stenosis.
 - g. - Uncontrolled heart failure.
 - h. - Acute pulmonary embolus or pulmonary infarction.
 - i. - Thrombosis of lower extremities.
 - j. - Suspected dissecting aneurysm.
 - k. - Uncontrolled asthma.

- l. - Pulmonary edema.
- m. - Room air desaturation at rest $\leq 85\%$
- n. - Respiratory failure.
- o. - Acute no cardiopulmonary disorder that may affect exercise performance or be aggravated by exercise (i.e. infection, renal failure, thyrotoxicosis)
- p. - Mental impairment leading to inability to cooperate.

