The participants will be able to rest for about 20 minutes between each test and we will offer them refreshments. Oxygen will be supplied, when needed, via nasal cannula and titrated to maintain a $SpO_2 \geq 88\%$.

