4.8 RANDOMISATION

Following confirmation of eligibility by the CI or PI and signature of the informed consent, patients will be randomised using sealed letters to HIIT plus HFNO or HIIT plus nasal cannula. Patients will be sequentially randomised. Randomisation code and sealing of envelopes will be done by the research nurses and stored in a room at RIE and Royal

Victoria Infirmary accessible with a key. This will be done before any baseline procedures.

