4.10 INTERVENTION

The intervention consists of HIIT plus HFNO versus HIIT plus oxygen delivered through a nasal cannula. The oxygen delivered via HFNO will be between 31 and 37°C according to patient preference. To minimize condensation, the heated humidified gas is delivered via heated tubings through a wide-bore nasal prong. Air flow will be 50 L/min and FiO2 will be titrated to maintain SpO2 above 88%. The comparator will be oxygen delivered via nasal cannula titrated to the same SpO2. Both HIIT will be performed at the same workload, which will be progressive throughout the 8 weeks and will be modified during each session in order to achieve a Borg score of 5, starting with high load intervals at 60% of the maximal watts achieved beforehand during a maximal CPET divided by lower load intervals at 40% maximum load during the first week, and finishing with high load intervals at 110% maximum load separated by load intervals at 80% maximum load in the last weeks (see Appendix A and C).

Basically the participants will have to pedal in a stationary bicycle for 30 minutes, during the other 20 minutes the patients will do exercises for their upper limbs using Thera bands and dumbbells. Muscles of upper limbs to work will be deltoids, pectorals and biceps (3 series of 10 repetitions each). Finally the participants will receive 10 minutes of respiratory physiotherapy including techniques to eliminate phlegm, breathing exercises and ludic activities to train the respiratory muscles such as inflating balloons.

Which group will use HFNO or conventional oxygen will be randomly selected from a sealed envelope. Randomized means that all participants will have the same chance of belonging to one group or another, they must choose a sealed envelope and inside it will be written to which group they will belong.

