4.11 DURATION OF THE STUDY

In general, the study will consist of 8 weeks of intervention plus 1 day of evaluations before and after the intervention. The window between the baseline appointment and the first day of the intervention can be from 1 to 30 days, and the window between the last day of intervention and the post intervention appointment will be from 8 to 38 days.

Assessment	Screening	Baseline Appointment	To be done at home	Intervention (8 weeks)	Post-Intervention Appointment
-------------------	-----------	----------------------	--------------------	----------------------------	-------------------------------

		(1 st day before Intervention)	(Pre &Post Intervention)		(1 st day after Intervention)
Assessment of eligibility criteria	X				
Written informed consent	X				
Demographic data, contact details	X				
Randomisation	X				
Weight		X			X
Height		X			
Blood Test		X			X
Blood Pressure		X			X
QMVCT		X			X
mMRC		X			X
CPET		X			X
CWRCT		X			X
Physical activity levels in daily life			X		
SGRQ (Questionnaire)			X		
HADS (Questionnaire)			X		
Intervention 1 st Group HIIT + HFNO				X	
Intervention 2 nd Group HIIT + NC				X	

Observation: There will be continual ECG monitoring during all the tests.

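### Four of the six absolute HFNO contraindications in Appendix C are not named in the eligibility criteria, and one is covered by none, so a patient who may not receive HFNO can be randomised to it (minor)

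*Protocol*

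**What the plan says.** Section 4.10 defines the experimental treatment as interval training with HFNO through a wide-bore nasal prong, and for the procedure points the reader to the appendices ("see Appendix A and C"). Appendix C gives six absolute contraindications to HFNO, among them "Nasal passage abnormalities or recent nasal surgery". Under equipment it adds: "A mask could be used if other options are not appropriate". For the comparator, Appendix C states only the saturation target and lists no contraindications.

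Section 4.4 excludes on emphysema extent, FEV1/FVC ratio and co-enrolment (items 1 to 3). Item 4 then excludes on contraindications to a different procedure: "Absolute contraindications for cardiopulmonary exercise testing, which are" the sixteen entries a to p. Entry n is respiratory failure. Entry o reads "Acute no cardiopulmonary disorder that may affect exercise performance or be aggravated by exercise", with infection as one of its examples.

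On the order of events, section 4.8 says: "Following confirmation of eligibility by the CI or PI and signature of the informed consent, patients will be randomised using sealed letters". The same section puts this before any baseline procedure, and the schedule in 4.11 places it at screening. At the test visits, section 4.7 says: "Oxygen will be supplied, when needed, via nasal cannula and titrated". Section 4.11 adds: "The window between the baseline appointment and the first day of the intervention can be from 1 to 30 days".

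**The concern.** The eligibility criteria should ensure that every randomised patient could receive either treatment. Here the protocol says in one place who may not have HFNO and in another who may be randomised to it, and the two lists do not match.

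Two things are at stake:

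- **The comparison.** A contraindication found after allocation affects only the HFNO arm, because no such list applies to nasal cannula. A patient who cannot be given the allocated treatment either stays in the arm untreated, which dilutes the contrast, or is withdrawn, which removes from one arm a kind of patient who stays in the other.
- **Safety.** If the list is not consulted at set-up, a patient could receive a treatment that the protocol itself calls absolutely contraindicated.

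**Working it through.** **Step 1. Compare each contraindication with every criterion in 4.3 and 4.4.**

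| Appendix C item | Criterion that reaches it | Result |
|---|---|---|
| Type 2 respiratory failure needing NIV | Exclusion 4n (respiratory failure) | Covered |
| COVID, known or suspected | Exclusion 4o (infection); four-week stability requirement in inclusion 1 | Largely covered |
| Abnormal nasal passages or a recent nasal operation | None | Not covered |
| CSF leak | 4o if acute and read broadly; inclusion 3 only if a neurological impairment restricts mobility | At best partly |
| Basal skull fracture | As for CSF leak | At best partly |
| Severe epistaxis | 4o if active and judged to be aggravated by exercise | At best partly |

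The count is 2 + 1 + 3 = 6. The nasal item escapes 4o because a structural abnormality is not an acute disorder and past surgery is not a disorder at all. Neither 4.3 nor 4.4 has a general clause for patients whom the investigator considers unsuitable.

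**Step 2. Look for a later check before allocation.** Eligibility and consent are the only conditions in 4.8. Oxygen at the baseline tests is by nasal cannula, and those tests follow randomisation anyway. HFNO is first needed at the first training session, 1 to 30 days after the baseline appointment. The set-up steps in Appendix C cover consent, protective equipment, assembly and an alarm test, and include no step to check contraindications. Section 4.6 lets the investigator withdraw a patient, but for this problem that comes after allocation.

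**Step 3. Size.** The protocol has no figure to reproduce. It gives neither the prevalence of these conditions nor the arm sizes; the 15 in section 4.2 is per site. I assume n = 15 in the HFNO arm (half of about 30). I take p as the proportion of otherwise eligible patients with an uncovered contraindication, from 0.1% to 5%.

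Expected number = n × p. Chance of at least one = 1 − (1 − p)^15. Chance of at most one = (1 − p)^15 + 15p(1 − p)^14. Expected extra screen failures among 30 = 30 × p.

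| Assumed p | Expected in HFNO arm | At least one | At most one | Extra screen failures |
|---|---|---|---|---|
| 0.1% | 0.015 | 1.5% | over 99.9% | 0.03 |
| 1% | 0.15 | 14% | 99% | 0.3 |
| 2% | 0.30 | 26% | 96% | 0.6 |
| 5% | 0.75 | 54% | 83% | 1.5 |

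For example, at p = 1%: 15 × 0.01 = 0.15, and 1 − 0.99^15 = 0.1399. One such patient would be 1/15 = 6.7% of the assumed arm.

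**The case against.** The strongest reply is that the protocol never tells anyone to give HFNO to a contraindicated patient. The list is in the protocol, in the appendix that governs set-up, and section 11.2.2 makes the investigator responsible for knowing the protocol and informing staff. Harm therefore needs an oversight. This stands, and it limits the safety part of the point to the case where the list is missed. It does not answer the allocation part: staff who follow every section exactly can still allocate HFNO to a patient and then find that Appendix C bars it.

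A second reply is the mask. For a purely nasal problem a different interface might be workable, so withholding may not always follow. But the mask appears as an equipment note, section 4.10 specifies a nasal prong, and nowhere does the protocol say that a mask lifts an absolute contraindication. The document leaves this unsettled.

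Third, the conditions are likely to be rare among patients fit for maximal cycling and recruited from rehabilitation referrals or an ILD clinic, and Appendix C reads largely as a general device procedure. Both points stand, and they are why the severity is minor.

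A reader might infer more: that 4.4 screens only for exercise-test contraindications and omits the HFNO list altogether. The text does not support this. Exclusions 1 to 3 are of another kind, two of the six HFNO items are largely covered, and three may be partly reached.

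**Conclusion.** The point holds in a narrow form. One absolute HFNO contraindication is covered by no eligibility criterion, and three more are not named and are at best partly reached. Randomisation proceeds without checking any of them against Appendix C. The consequence is possible non-receipt or withdrawal in the HFNO arm only, or a safety breach if the list is overlooked.

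The number affected is unknown and probably zero or one. That rests on an assumed arm of 15 and assumed prevalences. The 54% chance of at least one case follows only from the highest of these and should not be read as a forecast. Allocation balance is not affected, and the documents do not support a claim that the primary comparison is materially biased. Severity is minor. The text available has no section 8, but 4.3, 4.4 and 4.8, on which the point rests, are there.

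**What to change.** Add one exclusion to section 4.4: any absolute contraindication to HFNO listed in Appendix C. Put the same line on the eligibility check that the CI or PI completes under 4.8, to be confirmed for every patient, whichever arm follows, before the envelope is opened. If the investigators consider a mask acceptable for some nasal conditions, Appendix C should say which.

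The cost is a few lines of text and, on the assumptions above, 0.03 to 1.5 expected extra screen failures among 30 patients, so possibly one or two. Conditions that arise after randomisation would still need a check at set-up.
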